#### **12.4. Patient Recruitment**

Advertisements approved by IRBs/ECs and investigator databases may be used as recruitment procedures.

Pfizer will have an opportunity to review and approve the content of any study recruitment materials directed to potential study patients before such materials are used.

#### **12.5. Reporting of Safety Issues and Serious Breaches of the Protocol or ICH GCP**

In the event of any prohibition or restriction imposed (ie, clinical hold) by an applicable competent authority in any area of the world, or if the investigator is aware of any new information that might influence the evaluation of the benefits and risks of the investigational product, Pfizer should be informed immediately.

In addition, the investigator will inform Pfizer immediately of any urgent safety measures taken by the investigator to protect the study patients against any immediate hazard, and of any serious breaches of this protocol or of ICH GCP that the investigator becomes aware of.

### **13. DEFINITION OF END OF TRIAL**

End of trial is defined as last subject last visit (LSLV).

### **14. SPONSOR DISCONTINUATION CRITERIA**

In the event of a Grade 4 or Grade 5 AE of Special Interest (meeting criteria for serious), such as cardiac or neurologic toxicity, enrollment and dosing in the study will pause, to allow for a thorough internal safety evaluation, possible external safety analysis and recommendations, and communication with the FDA. Enrollment and dosing will begin in the study only after agreement with the FDA.

Premature termination of this study may occur because of a regulatory authority decision, change in opinion of the IRB/EC, investigational product problems, or at the discretion of Pfizer. In addition, Pfizer retains the right to discontinue development of PrCa VBIR at any time. If a study is prematurely terminated or discontinued, Pfizer will promptly notify the investigator. After notification, the investigator must contact all participating patients and the hospital pharmacy (if applicable) within a time period set by Pfizer. As directed by Pfizer, all study materials must be collected and all CRFs completed to the greatest extent possible.

## 15. PUBLICATION OF STUDY RESULTS

### 15.1. Communication of Results by Pfizer

Pfizer fulfills its commitment to publicly disclose clinical trial results through posting the results of studies on [www.clinicaltrials.gov](http://www.clinicaltrials.gov) (ClinicalTrials.gov), the European Clinical Trials Database (EudraCT), and or [www.pfizer.com](http://www.pfizer.com), and other public registries in accordance with applicable local laws/regulations.

In all cases, study results are reported by Pfizer in an objective, accurate, balanced, and complete manner and are reported regardless of the outcome of the study or the country in which the study was conducted.

#### [www.clinicaltrials.gov](http://www.clinicaltrials.gov)

Pfizer posts clinical trial US Basic Results on [www.clinicaltrials.gov](http://www.clinicaltrials.gov) for Pfizer-sponsored interventional studies (conducted in patients) that evaluate the safety and/or efficacy of a Pfizer product, regardless of the geographical location in which the study is conducted. US Basic Results are submitted for posting within 1 year of the primary completion date for studies in adult populations or within 6 months of the primary completion date for studies in pediatric populations.

Primary completion date is defined as the date that the final patient was examined or received an intervention for the purposes of final collection of data for the primary outcome, whether the clinical study concluded according to the prespecified protocol or was terminated.

#### EudraCT

Pfizer posts EU Basic Results on EudraCT for all Pfizer-sponsored interventional studies that are in scope of EU requirements. EU Basic Results are submitted for posting within 1 year of the primary completion date for studies in adult populations or within 6 months of the primary completion date for studies in pediatric populations.

#### [www.pfizer.com](http://www.pfizer.com)

Pfizer posts Public Disclosure Synopses (clinical study report synopses in which any data that could be used to identify individual patients have been removed) on [www.pfizer.com](http://www.pfizer.com) for Pfizer-sponsored interventional studies at the same time the US Basic Results document is posted to [www.clinicaltrials.gov](http://www.clinicaltrials.gov).

### 15.2. Publications by Investigators

Pfizer supports the exercise of academic freedom and has no objection to publication by principal investigator of the results of the study based on information collected or generated by principal investigator, whether or not the results are favorable to the Pfizer product. However, to ensure against inadvertent disclosure of confidential information or unprotected inventions, the investigator will provide Pfizer an opportunity to review any proposed publication or other type of disclosure of the results of the study (collectively, "Publication") before it is submitted or otherwise disclosed.

The investigator will provide any publication to Pfizer at least 30 days before they are submitted for publication or otherwise disclosed. If any patent action is required to protect intellectual property rights, the investigator agrees to delay the disclosure for a period not to exceed an additional 60 days.

The investigator will, on request, remove any previously undisclosed confidential information before disclosure, except for any study- or Pfizer product-related information necessary to the appropriate scientific presentation or understanding of the study results.

If the study is part of a multicenter study, the investigator agrees that the first publication is to be a joint publication covering all study sites, and that any subsequent publications by the principal investigator will reference that primary publication. However, if a joint manuscript has not been submitted for publication within 12 months of completion or termination of the study at all participating sites, the investigator is free to publish separately, subject to the other requirements of this section.

For all publications relating to the study, Institution will comply with recognized ethical standards concerning publications and authorship, including Section II - "Ethical Considerations in the Conduct and Reporting of Research" of the Uniform Requirements for Manuscripts Submitted to Biomedical Journals, <http://www.icmje.org/index.html#authorship>, established by the International Committee of Medical Journal Editors.

Publication of study results is also provided for in the CSA between Pfizer and the institution. In this section entitled **Publications by Investigators**, the defined terms shall have the meanings given to them in the CSA.

If there is any conflict between the CSA and any Attachments to it, the terms of the CSA control. If there is any conflict between this protocol and the CSA, this protocol will control as to any issue regarding treatment of study patients, and the CSA will control as to all other issues.

## Appendix 1. Abbreviations

This is a list of abbreviations that may be used in the protocol.

Abbreviation	Term
AChR	Acetylcholine receptor
ADA	Anti-drug Antibody
ADT	Androgen Deprivation Therapy
AdC68	Adenovirus C68
ADR	Adverse Drug Reaction
AE	Adverse Event
ALK	Anaplastic Lymphoma Kinase
ALT	Alanine Aminotransferase
AST	Aspartate Aminotransferase
AUC	Area Under the Concentration-Time Curve
AUC tau	Area Under the Serum Concentration-time Curve Over the Dosing Interval
CCI	
BP	Blood Pressure
BCR	Biochemical Relapse
CBC	Complete Blood Count
CD	Cluster of Differentiation
CI	Confidence Interval
CL/F	Apparent Clearance
CLss/F	Clearance at steady state
C max	Maximum Drug Concentration
CR	Complete Response
CRF	Case Report Form
CRPC	Castrate Resistant Prostate Cancer
CT	Computed Tomography
CCI	
CTLA4	Anti-cytotoxic T Lymphocyte-associated antigen 4
cTnI	Cardiac troponin I
C trough	Trough Concentrations after Multiple Dosing
CYP450	Cytochrome P450 enzymes
DLT	Dose Limiting Toxicities
DMSO	Dimethyl-sulfoxide
DNA	Deoxyribonucleic Acid
ECG	Electrocardiogram
ECHO	Echocardiogram
ECOG	Eastern Cooperative Oncology Group
EGFR	Epidermal Growth Factor Receptor
FDA	Food and Drug Administration
FoxP3	Forkhead box P3

Abbreviation	Term
GCP	Good Clinical Practice
GGT	Gamma-glutamyltransferase
GnRh	Gonadotropin-releasing Hormone
HIV	Human Immunodeficiency Virus
HR	Hazard Ratio
IB	Investigator's Brochure
ICAM-1	Intercellular Adhesion Molecule-1
ICOS	Inducible T-cell costimulator
IgG4	Immunoglobulin type G4
IHC	Immunohistochemistry
IFN	Interferon
IM	Intramuscular
IND	Investigational New Drug
INR	International Normalized Ratio
IP	Investigational Product
irRECIST	Immune-Related Response Evaluation Criteria in Solid Tumors
IV	Intravenous
LAG3	Lymphocyte activation gene 3
CCI	[REDACTED]
LFA-3	Lymphocyte Function-Associated Antigen 3
MAb	Monoclonal antibody
MDSC	Myeloid Derived Suppressor Cell
mCRPC	Metastatic Castrate Resistant Prostate Cancer
MHC	Major Histocompatibility Complex
MFD	Maximum Feasible Dose
MFS	Metastasis-free Survival
MG	Myasthenia gravis
mTPI	Modified Toxicity Probability Interval
MRI	Magnetic Resonance Imaging
MTD	Maximum Tolerated Dose
MUGA	Multigated Acquisition Scan
MVA	Modified Vaccinia Virus Ankara
Nab	Neutralizing antibody
NHP	Non-Human Primates
NCI CTCAE	National Cancer Institute Common Terminology Criteria for Adverse Events
NOAC	New oral anticoagulant
NSCLC	Non-Small Cell Lung Cancer
CCI	[REDACTED]
ORR	Objective Response Rate
OS	Overall Survival
PBMC	Peripheral Blood Mononuclear Cell
PCWG3	Prostrate Cancer Working Group 3

Abbreviation	Term
CCI	[REDACTED]
PD-1	Programmed cell death protein-1
PD-L1	Programmed death-ligand 1
PD-L2	Programmed death-ligand 2
pDNA	Plasmid DNA
PFS	Progression Free Survival
PK	Pharmacokinetics
PR	Partial Response
PrCa	Prostate Cancer
PSA	Prostate Specific Antigen
PSADT	Prostate Specific Antigen Doubling Time
PSCA	Prostate Stem Cell Antigen
PSMA	Prostate-Specific Membrane Antigen
PT	Prothrombin Time
PTT	Partial Thromboplastin Time
Q3W	Every 3 Weeks
Q4W	Every 3 Weeks
QoL	Quality of Life
Rac	Accumulation ratio
RECIST	Response Evaluation Criteria in Solid Tumors
RP2D	Recommended Phase 2 Dose
rPFS	Radiographic Progression-free Survival
SAE	Serious Adverse Event
SARS-CoV2	Severe Acute Respiratory Syndrome CoronaVirus 2
SC	Subcutaneous
SOA	Schedule of Assessments
SRE	Skeletal Related Event
SRSD	Single Reference Safety Document
$t_{1/2}$	Half-life
TCR	T cell receptor
TEAEs	Treatment Emergent Adverse Events
$T_{max}$	Time to Maximum Concentration
TDS-IM	TriGrid Delivery System
TTPP	Time to PSA progression
UTN	Universal trial number
VBIR	Vaccine-based immunotherapy regimen
Vd/F	Apparent Volume of Distribution
VP	Virus Particles
WBC	White Blood Cell

**Appendix 2. ECOG Performance Status**

Grade	ECOG Performance Status
0	Fully active, able to carry on all pre-disease performance without restriction.
1	Restricted in physically strenuous activity but ambulatory and able to carry out work of a light or sedentary nature, eg, light house work, office work.
2	Ambulatory and capable of all self-care but unable to carry out any work activities. Up and about more than 50% of waking hours.
3	Capable of only limited self-care, confined to bed or chair more than 50% of waking hours.
4	Completely disabled. Cannot carry on any self-care. Totally confined to bed or chair.
5	Dead.

\*As published in Am J Clin Oncol 5:649 655, 1982.

## **Appendix 3. RECIST (Response Evaluation Criteria In Solid Tumors) version 1.1 Guidelines**

*Adapted from E.A. Eisenhauer, et al: New response evaluation criteria in solid tumours: Revised RECIST guideline (version 1.1). European Journal of Cancer 45 (2009) 228–247.*

### **CATEGORIZING LESIONS AT BASELINE**

#### **Measurable Lesions**

Lesions that can be accurately measured in at least one dimension.

- Lesions with longest diameter twice the slice thickness and at least 10 mm or greater when assessed by CT or MRI (slice thickness 5-8 mm).
- Lesions with longest diameter at least 20 mm when assessed by Chest X-ray.
- Superficial lesions with longest diameter 10 mm or greater when assessed by caliper.
- Malignant lymph nodes with the short axis 15 mm or greater when assessed by CT.

**NOTE: The shortest axis is used as the diameter for malignant lymph nodes, longest axis for all other measurable lesions.**

#### **Non-measurable disease**

Non-measurable disease includes lesions too small to be considered measurable (including nodes with short axis between 10 and 14.9 mm) and truly non-measurable disease such as pleural or pericardial effusions, ascites, inflammatory breast disease, leptomeningeal disease, lymphangitic involvement of skin or lung, clinical lesions that cannot be accurately measured with calipers, abdominal masses identified by physical exam that are not measurable by reproducible imaging techniques.

- Bone disease (based on PCWG3 criteria): Bone disease is defined as present or absent and will be followed as non-target lesions.
- Previous local treatment: A previously irradiated lesion (or lesion patiented to other local treatment) is non-measurable unless it has progressed since completion of treatment.

#### **Normal sites**

- Cystic lesions: Simple cysts should not be considered as malignant lesions and should not be recorded either as target or non-target disease. Cystic lesions thought to represent cystic metastases can be measurable lesions, if they meet the specific definition above. If non-cystic lesions are also present, these are preferred as target lesions.

- Normal nodes: Nodes with short axis <10 mm are considered normal and should not be recorded or followed either as measurable or non-measurable disease.

## **Recording Tumor Assessments**

All sites of disease must be assessed at baseline. Baseline assessments should be done as close as possible prior to study start. For an adequate baseline assessment, all required scans must be done within 28 days prior to treatment and all disease must be documented appropriately. If baseline assessment is inadequate, subsequent statuses generally should be indeterminate.

### **Target lesions**

All measurable lesions up to a maximum of 2 lesions per organ, 5 lesions in total, representative of all involved organs, should be identified as target lesions at baseline. Target lesions should be selected on the basis of size (longest lesions) and suitability for accurate repeated measurements. Record the longest diameter for each lesion, except in the case of pathological lymph nodes for which the short axis should be recorded. The sum of the diameters (longest for non-nodal lesions, short axis for nodal lesions) for all target lesions at baseline will be the basis for comparison to assessments performed on study.

- If two target lesions coalesce the measurement of the coalesced mass is used. If a large target lesion splits, the sum of the parts is used.
- Measurements for target lesions that become small should continue to be recorded. If a target lesion becomes too small to measure, 0 mm should be recorded if the lesion is considered to have disappeared; otherwise a default value of 5 mm should be recorded.

**NOTE: When nodal lesions decrease to <10 mm (normal), the actual measurement should still be recorded.**

### **Non-target disease**

All non-measurable disease is non-target. All measurable lesions not identified as target lesions are also included as non-target disease. Measurements are not required but rather assessments will be expressed as ABSENT, INDETERMINATE, PRESENT/NOT INCREASED, INCREASED. Multiple non-target lesions in one organ may be recorded as a single item on the case report form (eg, 'multiple enlarged pelvic lymph nodes' or 'multiple liver metastases').

## **OBJECTIVE RESPONSE STATUS AT EACH EVALUATION**

Disease sites must be assessed using the same technique as baseline, including consistent administration of contrast and timing of scanning. If a change needs to be made the case must be discussed with the radiologist to determine if substitution is possible. If not, subsequent objective statuses are indeterminate.

### **Target disease**

- Complete Response (CR): Complete disappearance of all target lesions with the exception of nodal disease. All target nodes must decrease to normal size (short axis <10 mm). All target lesions must be assessed.
- Partial Response (PR): Greater than or equal to 30% decrease under baseline of the sum of diameters of all target measurable lesions. The short diameter is used in the sum for target nodes, while the longest diameter is used in the sum for all other target lesions. All target lesions must be assessed.
- Stable: Does not qualify for CR, PR or Progression. All target lesions must be assessed. Stable can follow PR only in the rare case that the sum increases by less than 20% from the nadir, but enough that a previously documented 30% decrease no longer holds.

- Indeterminate. Progression has not been documented, and
  - One or more target measurable lesions have not been assessed;
  - Or assessment methods used were inconsistent with those used at baseline;
  - Or one or more target lesions cannot be measured accurately (eg, poorly visible unless due to being too small to measure);
  - Or one or more target lesions were excised or irradiated and have not reappeared or increased.

### **Non-target disease**

- CR: Disappearance of all non-target lesions and normalization of tumor marker levels. All lymph nodes must be 'normal' in size (<10 mm short axis).
- Non-CR/Non-PD: Persistence of any non-target lesions and/or tumor marker level above the normal limits.
- PD: Unequivocal progression of pre-existing lesions. Generally the overall tumor burden must increase sufficiently to merit discontinuation of therapy. In the presence of SD or PR in target disease, progression due to unequivocal increase in non-target disease should be rare.

- Indeterminate: Progression has not been determined and one or more non-target sites were not assessed or assessment methods were inconsistent with those used at baseline.

### **New Lesions**

The appearance of any new unequivocal malignant lesion indicates PD. If a new lesion is equivocal, for example due to its small size, continued assessment will clarify the etiology. If repeat assessments confirm the lesion, then progression should be recorded on the date of the initial assessment. A lesion identified in an area not previously scanned will be considered a new lesion.

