12. **Coagulation:** Should include Prothrombin Time (PT) or International Normalized Ratio (INR) and Partial Thromboplastin Time (PTT). Samples will be analyzed locally.
13. **Cardiac Troponin:** For participants undergoing screening, circulating levels of cardiac Troponin-I (cTnI) must be measured and found to be within the normal reference range within 28 days before study entry, preferably using the central laboratory kits provided. See [Section 7.1.7](#) for full details.
14. **Urinalysis:** Dipstick is acceptable. Microscopic analyses if dipstick abnormal. Samples will be analyzed locally.
15. **Triplicate 12 leads ECGs:** At each time point, three consecutive 12-lead ECGs will be performed approximately 2 minutes apart to determine mean QTcF interval. If the mean QTcF is prolonged (>500 msec), the ECGs should be re-evaluated by a qualified person at the institution for confirmation. Additional triplicate ECGs may be performed as clinically indicated.
16. **Registration:** Participant number and dose level allocation operated by Pfizer Inc.
17. **Investigational Product Administration:** Treatment to be administered after all other assessments required on that day have been performed.
18. **Tumor Assessments:** Tumor assessments will include all known or suspected disease sites. Screening images may be obtained within 5 weeks of registration. Imaging obtained as part of standard of care but within 28 days (-7 days) of registration may be used for screening assessment. Imaging may include chest, abdomen and pelvis CT or MRI scans or bone scans. Bone scans will be performed at baseline if disease is suspected and on-study as appropriate to follow disease. Baseline central nervous system (CNS) imaging is not required with the exception of symptomatic participants to rule out CNS metastases. CT or MRI scans, as well as bone scans, when indicated, are to be done every 8 weeks ( $\pm$  5 days) with the first one to occur 8 weeks after C1D1 until disease progression that requires new treatment modality, permanent discontinuation, or death. Disease progression will be confirmed with two consecutive timepoints at least 4-6 weeks apart in the absence of rapid clinical deterioration. Tumor assessment should be repeated at the End of Treatment visit if more than 6 weeks have passed since the last evaluation. **CCI** [REDACTED]  
[REDACTED]  
[REDACTED]

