## Appendix 5. Guidelines for Evaluation of Bone Scans

*Based on Prostate Cancer Working Group 3.*

An international expert committee of prostate cancer clinical investigators (the Prostate Cancer Clinical Trials Working Group 3 [PCWG3]) was reconvened and expanded and met in 2012-2015 to formulate updated criteria on the basis of emerging trial data and validation studies of the Prostate Cancer Clinical Trials Working Group 2 recommendations.

Given the frequency of bone involvement in patients with progressive, castration-resistant disease, the decreased emphasis of early changes in PSA, and the increased availability of cytostatic agents, reliable methods to assess changes in bone are of increasing importance. PCWG3 recognizes that standards for using MRI and PET to assess bone metastases are under active investigation, so only radionuclide bone scans are considered here. PCWG3 also recognizes that there are no validated criteria for response on radionuclide bone scan.

For control/relieve/eliminate end points, the PCWG3 recommends that post-treatment changes be recorded “no new lesions,” “new lesions” or “resolved bone lesion.” However, progression at the first scheduled assessment should be confirmed on a second scan performed 6 or more weeks later, in the absence of clearly worsening disease or disease-related symptoms. In the event of visible lesions disappearing, this should also be confirmed at the next scheduled assessment.

For prevent/delay end points, progressing disease on bone scan is considered when at least two new lesions relative to the first post-treatment scan is confirmed on a subsequent scan. PCWG3 does not recommend performing a follow-up bone scan before 12 weeks of treatment unless clinically indicated. At the first 12-week reassessment, defining disease progression requires a confirmatory scan (which shows additional new lesions compared with the first follow-up scan) performed 6 or more weeks later, because lesions visible at the first 12-week assessment may represent disease that was not detected on the pretreatment scan. When further progression is documented on the confirmatory scan, the date of progression recorded for the trial, is the date of the first scan that shows the change.

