Selected ad-hoc efficacy analyses (eg, ORR and radiographic PFS) combining participants from Cohorts 7A and 3B may be conducted, as participants in those two cohorts have identical or similar eligibility criteria for study entry and are scheduled to receive the same regimen.

Swimmer plots may be used to display duration of treatment and tumor response at each applicable time point. Waterfall plot for individual tumor size percent change from baseline, and spider plot for individual tumor size percent change from baseline over time may be presented. These plots, if generated, will be presented for RECIST 1.1 and irRECIST separately.

For the rPFS analysis in Part B, the Kaplan-Meier analysis may be performed if deemed necessary. If the Kaplan-Meier analysis is performed for radiographic progression-free survival, an event is defined as the first occurrence of “PD” status by investigator, or death, or a PCWG3 defined bone disease progression, whichever comes first, under RECIST. Time zero for all time-to-event analyses will be defined as the first vaccination on Cycle 1 Day 1. This analysis may be performed for the combined cohorts 7A and 3B. CCI

For duration of response per RECIST and time to response (from the first vaccination date to the time of the first response, CR or PR) in Part B, descriptive statistics will be provided. Kaplan-Meier analysis may be performed if deemed necessary. These analyses may be performed for the combined cohorts 7A and 3B.

PSA kinetics

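### One bone lesion first seen at week 8 can be an rPFS event under Appendix 3 RECIST but not under the PCWG3 bone rule, and the visible plan does not say which governs

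*Protocol*

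**What the plan says.** **RECIST rules (Protocol Appendix 3).** On bone, the non-measurable disease section says: "Bone disease is defined as present or absent and will be followed as non-target lesions". That bullet opens by naming PCWG3 as its basis. Under New Lesions, one unequivocal malignant new lesion is enough for PD, and "A lesion identified in an area not previously scanned will be considered a new lesion". The last row of both response tables gives PD whenever a new lesion is present, whatever the other entries.

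**Bone rules.** Protocol Sections 7.4 and 9.4 name PCWG3 as the criteria for bone disease. Appendix 5 requires at least two new lesions compared with the first post-treatment scan, confirmed later. Its reason is that "lesions visible at the first 12-week assessment may represent disease that was not detected on the pretreatment scan".

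**Imaging (Schedule of Activities for the expansion cohorts, tumor assessment footnote).** "Bone scans will be performed at baseline if disease is suspected and on-study as appropriate to follow disease". On study, "CT or MRI scans, as well as bone scans, when indicated, are to be done every 8 weeks", starting 8 weeks after Cycle 1 Day 1.

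**Entry (Protocol Section 4.1.2, criterion 18).** PSA progression, measurable disease and new bone-scan lesions are alternatives, so PSA alone suffices.

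**Endpoint (SAP 8.1.3).** An rPFS event is the first of investigator PD, death, "or a PCWG3 defined bone disease progression, whichever comes first, under RECIST". SAP 4.3 calls rPFS the key supportive efficacy endpoint for Cohort 3B.

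**The concern.** Two rules for bone sit side by side, and the endpoint takes whichever fires first. Appendix 5 guards against counting disease that was there before treatment. The unscanned-area sentence in Appendix 3 does the reverse: it turns a lesion nobody had looked for into a new one.

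The exposed participant is one whose entry rested on PSA or nodal disease, who had no suspected bone disease and so no baseline bone scan, and who is scanned at week 8, for example because PSA is rising. Protocol Section 1.3.1 says most metastatic lesions in prostate cancer are in bone and lymph nodes, so the case is not far-fetched. If the lesion predates treatment, disease present at entry is dated as treatment failure at the first assessment. Whether that happens depends on who had a baseline scan and which appendix the investigator followed. Two analysts could then obtain different rPFS curves from the same images.

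**Working it through.** **Plan's own figures.** The plan states no rPFS sample size, event count or power. Its one numerical example for Cohort 3B concerns ORR: 6 of 18 responders with a Beta(0.5, 0.5) prior give a Beta(6.5, 12.5) posterior, and P(ORR > 25%) = 0.797. This agrees with the stated figure of about 80%. The present point does not depend on it.

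**Rule trace.** Take one stable bone lesion, unequivocal, first seen on a week-8 bone scan, with no baseline bone scan.

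| Rule applied | Result at week 8 |
|---|---|
| Appendix 3, New Lesions and the response tables, read literally | PD, hence an rPFS event |
| Appendix 5 (PCWG3): one lesion is fewer than two, and this scan is itself the reference | No event |
| Appendix 3, inadequate baseline: later statuses generally indeterminate | No event |
| Appendix 4 (irRECIST): a new non-measurable lesion does not define progression | No event |

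The visible text does not rank these rules. Confirmation does not settle it either. The Schedule of Activities says "Disease progression will be confirmed with two consecutive timepoints at least 4-6 weeks apart in the absence of rapid clinical deterioration", but a stable pre-existing lesion would still be visible on the repeat scan and so would be confirmed.

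**Timing.** 8 × 7 = 56 days after Cycle 1 Day 1, with a ±5 day window: 51 to 61 days after, or study Days 52 to 62. Appendix 5 advises against a follow-up bone scan before 12 weeks unless clinically indicated, so the Schedule's first assessment falls earlier than that rule assumes.

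**Size.** With n = 18 and nobody censored before week 8, each extra event lowers the Kaplan-Meier estimate by 1/18 = 5.6 percentage points. The drop lasts for as long as that participant would otherwise have been event-free, and vanishes from the date he would have had an event anyway. If Cohorts 7A and 3B are pooled, with 14 participants (Protocol Section 1.3.2) and 18 (Section 3.1.2), it is 1/32 = 3.1 points.

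**Frequency.** The documents give none. As an illustration only, let s be the assumed share of participants with no baseline bone scan and an unseen bone lesion found at week 8. The expected count is 18s, and the chance of at least one is 1 − (1 − s)^18.

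| Assumed s | Expected count | P(at least one) |
|---|---|---|
| 2% | 0.36 | 0.31 |
| 5% | 0.9 | 0.60 |
| 10% | 1.8 | 0.85 |
| 20% | 3.6 | 0.98 |

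**The case against.** The best counter-argument is that the plan plainly means bone to be judged by PCWG3. Sections 7.4 and 9.4 say so, the Appendix 3 bone bullet begins with PCWG3, and SAP 8.1.3 lists PCWG3 bone progression separately. On the literal reading of Appendix 3 that separate limb would add nothing: two new bone lesions imply at least one, so single-lesion PD could never be dated later. This is good evidence of intent. It still does not tell an investigator to leave bone out of RECIST PD, and it leaves the new-lesion rows of the response tables in place.

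Other objections stand in part:

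- **Inadequate baseline.** Appendix 3 also wants all disease sites assessed at baseline and calls later statuses generally indeterminate when that baseline is inadequate. But its Indeterminate categories apply only where progression has not been documented, so they do not displace the PD rows.
- **Area already scanned.** A baseline CT of chest, abdomen and pelvis arguably covers much of the axial skeleton. That narrows the case but does not close it, because modality is left open: "Imaging may include chest, abdomen and pelvis CT or MRI scans or bone scans".
- **Excluding early progression.** Protocol Section 9.4 and SAP 8.1.3 allow progressions before, for example, Day 57 or Day 113 to be left out. A Day 113 cut would remove a week-8 event; a Day 57 cut would miss scans on Days 57 to 62. Both are optional, and both also discard genuine early progression.
- **Text not visible.** Much of Section 7.4 and the end of the SAP's rPFS paragraph are redacted, and SAP 10.3 defers rPFS programming to a separate specification. A ranking rule may exist there.

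A reader might also infer more than the documents support:

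- **That baseline bone scans are simply optional.** They are conditional on suspected disease.
- **That the PCWG3 rule never governs.** This assumes the literal reading that is in dispute.
- **That ORR falls, or a later response is blocked.** About 40% of Part B participants is the only minimum set for measurable disease, and partial response is not available to a participant with non-target disease only. SAP 8.1.3 takes best response across all assessments without stating a stop at RECIST PD.

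**Conclusion.** The concern holds as a conflict of rules with a limited reach. In the visible text, the same week-8 finding is an rPFS event under Appendix 3 and no event under Appendix 5, and SAP 8.1.3 admits both routes. The consequence is a possibly wrong event date, which is more than a missing detail.

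The effect is up to 5.6 percentage points of RECIST-based rPFS after week 8 per affected participant in Cohort 3B. That assumes all 18 are analysed, none is censored earlier, and the participant would otherwise be event-free. The number affected cannot be derived from the documents, and the shares in the table are assumptions. irRECIST results are unaffected, and no ORR effect is claimed. The endpoint is secondary and descriptive, with no hypothesis test and a Kaplan-Meier analysis that is itself discretionary. The point should be corrected before rPFS is derived, but it does not threaten the trial's primary safety objective.

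**What to change.** In SAP 8.1.3 and Protocol Appendix 3, state for the mCRPC cohorts that:

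- within rPFS, RECIST PD and new lesions refer to soft tissue only;
- bone lesions enter rPFS only through the PCWG3 rule in Appendix 5;
- the unscanned-area sentence does not apply to bone scans;
- where there is no baseline bone scan, the first on-study bone scan is the reference for counting new lesions, which fits how Appendix 5 already counts;
- participants without a baseline bone scan are flagged in the rPFS listing.

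If the programming specification already says this, a cross-reference from SAP 8.1.3 is enough.

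The cost is wording, with no extra scans. Enrolment is closed, so baseline scanning cannot be changed. There are two drawbacks. Some bone progressions will be dated later. And because PD is assigned by the investigator, and Appendix 3 lets several non-target lesions in one organ be recorded as a single item, the site of a new lesion may have to be queried where the CRF does not separate bone from soft tissue.
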